4.	Upper or middle third ureteral stricture or stone AND/OR stone located in the renal pelvis				
5.	Patient agrees to participate in the study and signs the informed consent form				
6.	Able to complete self-rated questionnaires				

	Exclusion Criteria
1.	Patients with distal ureteral obstruction
2.	Patients with urinary reflux (assessed by pre-stent cystogram)
3.	Patients requiring bilateral surgical stone management procedure or patients with active

	urinary tract infection (UTI) or sepsis				
4.	Intraoperative exclusion: Based on the urologist's discretion, if trauma has been induced				
	to the distal ureter due to ureteroscopy maneuvers, exclude these patients.				

Number of Research Participants

We plan to enroll a minimum of 20 patients, not to exceed 30 patients at UHCMC.

Recruitment Methods

Following Institutional Review Board (IRB) approval of the proposed study, patients will be identified during their clinic visits to one of the Endourology providers at UH and will undergo a standard consultation to discuss all available treatment options. Patients who are deemed clinically suitable to undergo the RELIEF Stent and choose to participate will be screened utilizing the EMR for recruitment. The urology provider will first determine if they are interested in participating in the research study and upon agreement, a study team member or research coordinator will introduce the study details and initiate a consent interview. If eligible, these patients will be approached during pre-surgical preoperative clinic or inpatient visits by the research team to further explain the study and further address any of their questions and get their consent. Patients will be free to leave the study without any impact or influence on their clinical care or management at any point should they desire to do so.

Setting:

- UH Cleveland Medical Center, UH Richmond Medical Center, UH Ahuja Medical Center, UH St. John Medical Center, UH Brainard Medical Building ([name]), and UH Beachwood Medical Center
- 2) Patients will be identified during their clinic visits to one of the UH Endourology providers
- 3) UH main campus Lakeside: 4559 and UH Beachwood Medical Center

Consent Process

Eligible subjects will be consented by a Research Nurse or Investigator prior to the procedure.

Study subjects will be asked to sign the Informed Consent at the time of admission for procedure.

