All subjects should be familiar with the Informed Consent and its content, and have been given opportunity to have their questions answered about the study prior to signing the Informed Consent. At the time of admission, the patient will be assessed for suitability. If the patient meets the inclusion/exclusion criteria, he/she will enter the study.

Results will be shared with ONLY the research participants' doctors who are among the approved study team by the UH IRB.

Study Design

Allocation: Non-randomized

Endpoint Classification: Safety/Efficacy Study

Intervention Model: Single Group Assignment

Masking: Open Label

Primary Purpose: Treatment

Study Procedures

Informed Consent: Eligible subjects will be consented by a Research Nurse or Investigator prior to the procedure.

Inclusion Criteria: Confirmation of fulfilling Inclusion criteria (e.g., consent, examination, indication) and that subject does not have any Exclusion criteria.

Pre-Stenting Evaluation (Day 0 or within 24 hours of Day 0): USSQSurvey and 10 -Point Pain Score: Subject completesUSSQsurvey for baseline evaluation (pre-stenting, Day 0)

Ureteral Stenting Procedure (Day 0):

Pre-stent cystogram

- Instill dye (up to 300 cc) under gravity-filling cystogram for assessment of pre-stent reflux and capture Xray image (with C-arm). (Exclude patients with reflux). Cystogram image will be saved.
- Drain bladder

[CRF: Pre-Stent Reflux Result; Pre-Stent Cystogram Image]

Ureteral Stent Placement

- Obtain retrograde pyelogram.
- Insert guidewire and perform ureteroscopy for treatment when needed. (Based on the urologist's discretion, if trauma has been induced to the distal ureter due to ureteroscopy maneuvers, these patients will be excluded).

- Any remaining contrastshould be flushed by irrigation ofsaline. Confirmatory X-ray image may be captured to ensure that contrast has been adequately removed (Note: If residual contrast considered not acceptable or confirmatory X-ray not recommended, subject may be excluded from study and traditional stent used).
- Remove the pull-outsuture, then place RELIEF stent under cystoscopy. Stent with pusher placed over guidewire and inserted. Position pusher until reach 4 cm mark. Remove wire. Back-out pusher. Confirm xray image ofstent position and save the image.

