[Case Report Form (CRF): Acceptable cystoscopy visualization or unusual/unforeseen observation(s) noted. Acceptable result of retrograde pyelogram. Observations noted, if any. Cystoscopy image and X-ray image saved. Confirmatory X-ray shows no/low residual contrast, considered acceptable for Study.]

Post-stent cystogram

- Instill dye (up to 300 cc) under gravity-filling cystogram for assessment of post-stent reflux.
- Drain bladder.
- Fill bladder with 150 cc saline up to 300 cc to assess whether distal coil ofstent istouching trigone (documented as "on" or "off") at both volumes.
- Treat patient understandard of care.

CFR: DAY 0 – Stent Placement. X-Ray image; post-stent placement. Record post-stenting cystoscopy image, if possible. Record distal coil location. [CRF: Post-Stent Reflux Result; Post-Stent Cystogram Image]. Record Clinician Usability Survey results(from stenting placement procedure). [Considered: Day 0]

Post-stent Follow-Up:

- Post-operatively complete USSQ surveys at 24-48 hours post-stent placement, and at day 7-30 prior to removal of RELIEF stent.
- Day 1 (24-48 hours afterstenting procedure), subject will be evaluated by Clinician for acceptable procedural outcome.
- Subject will complete USSQ and 10-point pain scale surveys. [CRF: Successfully completed post-stent placement USSQ survey (attach) and record 10-Point Pain Score. Clinician examination results recorded as acceptable, no further intervention warranted.]
- Day ofstent removal: Prior to stent removal procedure on day 7-30, subject will be asked to complete stent in situ USSQ and 10-point pain scale surveys. Subject will then be examined by Clinician with cystoscope and standard X-ray, if warranted. Ureteral orifice (with stent) will be evaluated for potential signs of irritation or inflammation with photograph taken if possible, a scale of 0-1-2 (Normal, mild inflammation, and moderate inflammation) will be used to grade orifice appearance. Stent removal will be performed by a standard of care approach (in-office cystoscopic removal). Stent will be evaluated for signs of encrustation and/or visually observable damage / dislocation or wear. Photograph stent. Clinician survey will be completed to assess usability for removal. Economic metric of removal time may also be included, if possible.

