• If possible, subject will complete USSQ and 10-point pain scale surveys 1-2 days afterstent removal. If unusual level of pain or other potentially serious complications suspected, subject will be asked to come in for office visit and Clinician evaluation. [CRF: Record direct or remote subject evaluation and any unusual/ unexpected observation(s). Obtain successfully completed in situ USSQ survey (attach to CFR) and record 10-Point Pain Score. Record if subject directed to come in for clinician evaluation. Record post-stent evaluation and photograph, if possible. Record Clinician Usability Survey forstent removal. If possible, subject will complete post-stent removal USSQ survey (attach to CFR) and 10-Point Pain Score.] Afterseveral cases of the Relief Stent, an optional supplemental questionnaire may be completed by the provider regarding the use of the research device.

Study Timeline

Assessment	Screening and Stent Placement (Day 0)	Post-Stent Placement (24-48 hrs)	Day of Stent Removal (Stent in situ, Day 7-30)	Post-Stent Removal
Informed Consent Form	X			
General Physical Examination	х	X [In-office or remote evaluation]	X [In-office]	
Current Medications	х	X [In-office or remote evaluation]	X [In-office]	
Vital Signs	х	X [In-office or remote evaluation]	X [In-office]	
Indicated for Ureteral Stenting	X			
Inclusion/Exclusion Criteria	Х			
Enrollment	X			
Ureteral Stent Symptoms Questionnaire	х	х	X [Before removal]	X [In-person or remote evaluation
RELIEF® Ureteral Stent	X [Placement]		X [Removal]	
Additional Therapies, if needed	×	x	x	ľ
Adverse Events	X	х	X	
Clinician Usability Survey	X [Placement]		X [Removal]	

Data to be Collected

- Patient demographics (Age, Sex, Race, BMI)
- Present and past history.
- Prior surgical procedures.
- Laboratory tests results,
- Any imaging results on the abdomen and pelvis.
- USSQ survey.

B. Intra-operative

- Total operative time
- Total fluoroscopy time
- Case Report forms as described before.

C. Post-operative

- USSQ survey.
- Case Report forms.
- Any complications/ adverse events.

[figure not shown]
Data Analysis Plan

Current enrollment number is designed to collect sufficient patient data to power a future, statisticallypowered clinical study to obtain an expanded FDA intended use claim for reduction in reflux and minimizes the potential for coil positioning on the trigone.

Study Endpoints:

1- Primary effectiveness endpoint:

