- Study success defined as adequate short term drainage defined as the presence of the stent in the ureter and the lack of surgical or other intervention to treat symptoms associated with the stent itself or failure of the stent on the stented side during the first 48 hours [Day 0-2] following placement. [Note: In some cases, the ureteral stent may not be sufficient to relieve pain (not associated with stent specifically) and alternative surgical treatment may be warranted. In these cases, patient data will be captured but non-device related cause captured as reason for subject stenting termination.]
- Assessment of retrograde urine reflux after placement of the RELIEF® Ureteral Stent, as determined by the visualization of urine in the distal ureter to the kidney using cystography after contrast gravity-filling of the bladder and assigning a urinary reflux grade based on:
 - Grade I: urine refluxes into the ureter only.
 - Grade II: urine refluxes into the ureter and up to the kidney without dilation.
 - Grade III: urine refluxes into the ureter and kidney and causes mild dilation.
 - Grade IV: urine refluxes into ureter and kidney and causes dilation without twisting of the ureter.
 - Grade V: urine refluxes into ureter and kidney and causes significant dilation with twisting of the ureter.

• Visualization of distal coil in bladder, after RELIEF Stent placement. Document placement using a cystoscope.

2- Primary safety endpoint:

• Assessment of adverse events (incidence, relationship to device, severity) attributed to the Ureteral Stent, compared to established adverse event rates from published clinical studies and FDA reportable event occurrences, compared to number of US annual ureteral stent placements. (No anticipated adverse events from Stent design; known complications from stenting may be observed.)

3- Secondary endpoint:

• USSQ Scale (Ureteral Stent Symptoms Questionnaire) [Time Frame: Day 0 (pre-stenting), 24-48 hours post-stent placement, and Day 7-30 prior to stent removal].

Stopping Rules: In the occurrence of any unexpected adverse events to the participants, the study team will hold study recruitment until the investigation is completed. Patients who experience unanticipated adverse events will have the RELIEF stent promptly removed.

Expected Adverse Events include:

- Flank pain/loin discomfort
- Flank pain when voiding
- Suprapubic pain/lower abdominal pain
- Trigonal irritation
- Urinary frequency
- Nocturia
- Urinary urgency

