- Dysuria
- Urethral discomfort
- Incontinence

- Hematuria
- Stent migration
- Stent encrustation
- UTI
- Bacteriuria
- Signs of ureter trauma
- Additional stent specific procedures

Risks to Research Participants

There is a potential risk of loss of confidentiality of your data. Every effort will be made to keep the patients' information confidential.

The study participants may feel uncomfortable while addressing some of the questions in the pain questionnaire. They may refuse to answer any of these questions. They may stop their participation in this study at any time.

Ureteral stents are as a SoC procedure that is reported in the literature to be associated with adverse events including: • Flank pain/loin discomfort • Flank pain when voiding • Suprapubic pain/lower abdominal pain • Trigonal irritation • Urinary frequency • Nocturia • Urinary urgency • Dysuria • Urethral discomfort • Incontinence • Hematuria • Stent migration • Stent encrustation • UTI • Bacteriuria • Signs of ureter trauma • Additional stent specific procedures

In case any patient experiences any unexpected adverse events, the study team will hold study recruitment until the investigation is completed. Patients who experience unanticipated adverse events will have the RELIEF stent promptly removed.

Provisions to Protect the Privacy Interests of Research Participants

The study subjects will be reviewed in a private room or space and will be protected against viewing by any person either not on the study team or not currently caring directly for the subject. There will be no discussion outside closed doors regarding any information pertaining to data collected.

Potential Benefit to Research Participants

We assume that the potential benefits from participating in this study may include little to no backflow of urine to the kidney, less flank pain and less bladder irritative symptoms than the current standard of care. However, given that the stent is under investigation, these benefits cannot be guaranteed.

Withdrawal of Research Participants

Study participants will remain in the trial unless they choose to withdraw or they no longer meet the inclusion or exclusion criteria. Participants will be free to withdraw at any part of the study period without any influence on their treatment pathway or care.

Alternatives to Participation

If a patient chooses not to participate in this study, standard of care treatment will be provided.

Costs to Research Participants

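### Bacteriuria is an expected adverse event within a safety endpoint compared with published rates, but no urine test is scheduled after placement, so its rate is biased downward by an unknown amount

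*Protocol*

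**What the plan says.** **The event.** The Expected Adverse Events list under Study Endpoints, and the same list under Risks to Research Participants, give bacteriuria its own entry beside UTI: "Stent encrustation - UTI - Bacteriuria - Signs of ureter trauma".

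**Its use.** The primary safety endpoint (Study Endpoints, item 2) is the incidence, device relationship and severity of stent-attributed adverse events, "compared to established adverse event rates from published clinical studies and FDA reportable event occurrences". No rate, margin or denominator is given.

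**The design.** "Intervention Model: Single Group Assignment", with this size: "We plan to enroll a minimum of 20 patients, not to exceed 30 patients at UHCMC".

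**What is measured after placement.** At 24-48 hours and on the day of removal (day 7-30), the Study Timeline has physical examination, medications, vital signs, the USSQ and adverse events. The 24-48 hour assessment may be remote. There is no row for urinalysis or culture at any visit. In Data to be Collected, "Laboratory tests results" stands only in the first block, above the intra-operative one. That block's own heading is not visible, but its content is pre-operative. The post-operative block has the USSQ, case report forms and complications or adverse events.

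**How events come to light.** Under the data-monitoring section, subjects report adverse events to the coordinator or physician, and the adverse event form records the type of tests used. Study Procedures leaves care after placement to standard practice.

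**The concern.** A separate entry for bacteriuria adds something to UTI mainly when there are bacteria without a symptomatic infection. A patient cannot report that state, and neither examination, vital signs nor the USSQ can reveal it. It takes a urine test, and none is scheduled.

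In a randomised trial, under-detection would fall on both arms and largely cancel in the comparison. Here there is one arm and the comparator is the literature, so nothing balances it. A case not tested for enters the count as no event, and this error runs in the device's favour. The stake is how far the primary safety endpoint can reassure on infection. A low bacteriuria count could mean few cases or few tests, and the rate alone cannot tell these apart. No later analysis can recover urine results that were never obtained.

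**Working it through.** The Protocol states no bacteriuria rate, and its sample size has no calculation behind it, so there is no figure to reproduce. The following is an illustration of the mechanism.

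**Inputs**
- n = 20 to 30 (Number of Research Participants).
- p, the true proportion with bacteriuria: not in the documents. Assumed 20%, range 10-40%.
- q, the share of patients whose urine is tested off schedule: not in the documents. Varied from 0 to 100%.
- Assumptions: a perfect test, testing unrelated to bacteriuria, and all patients in the denominator. The Protocol does not state the last of these.

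**Formulas**
- Expected observed rate = p × q.
- Probability of recording no case = (1 − p × q)^n.
- Exact two-sided 95% upper limit for a count of 0 in n = 1 − 0.025^(1/n).

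**Results at p = 20%**

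| Share tested q | Expected observed rate | P(no case), n = 20 | P(no case), n = 30 |
|---|---|---|---|
| 0% | 0% | 100% | 100% |
| 25% | 0.20 × 0.25 = 5% | 0.95^20 = 35.8% | 0.95^30 = 21.5% |
| 50% | 0.20 × 0.50 = 10% | 0.90^20 = 12.2% | 0.90^30 = 4.2% |
| 100% | 20% | 0.80^20 = 1.2% | 0.80^30 = 0.1% |

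**Range.** For p from 10% to 40%, testing a quarter of patients gives an expected observed rate of 2.5% to 10%, and testing half gives 5% to 20%. An observed 5% is thus what one would expect from p = 20% with a quarter tested, or from p = 10% with half tested. The rate cannot be interpreted without the number tested.

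**Zero counts.** The upper limit is 1 − 0.025^(1/20) = 16.8% for 0/20 and 1 − 0.025^(1/30) = 11.6% for 0/30. If nobody were tested, either limit would lie below an assumed true 20%. Neither would lie below a true 10%.

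**If testing is not independent.** What matters is the share of patients with bacteriuria who are tested. If symptoms prompt the tests, that share may exceed q and the shortfall is smaller than tabulated. Cases without symptoms are then still missed unless routine care tests them.

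**The case against.** The strongest reply is that the Protocol does not rule urine testing out. Care follows standard practice, the adverse event form records tests used, and the Background puts stent symptoms at up to 80% of patients, which could prompt many tests. This stands. A reader might infer that the rate is near zero by design, but the documents support that only if few patients are tested, and they do not say how many will be.

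A reader might also infer that the device will look better than published rates. The Protocol gives neither those rates nor how they were obtained. If the published studies also tested only for cause, the difference could be small.

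Nor does the Protocol say that untested patients will be counted in the denominator. It speaks of incidence only, and the denominator may properly be left to a statistical analysis plan that is not shown. The all-patients denominator above is therefore an assumption.

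The adverse event list follows the stopping rule for unexpected events and may serve to separate expected from unexpected ones. It does not commit the trial to an item-by-item comparison. That is fair, but the endpoint as worded covers stent-attributed adverse events without exception, so bacteriuria is not excluded.

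Finally, the same criticism might seem to apply to stent migration, because of the wording at removal: "Subject will then be examined by Clinician with cystoscope and standard X-ray, if warranted". It does not carry over. An X-ray of stent position is saved at placement, removal is cystoscopic, and the removed stent is checked for dislocation, so position is looked at on schedule.

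**Conclusion.** The point holds in a limited form. Bacteriuria is a listed adverse event within a primary safety endpoint set against published rates, in one arm, with no scheduled urine test after placement. Its rate over all patients will be biased downward by an unknown amount and is not comparable with studies that tested everyone. With an assumed true rate of 20% and testing unrelated to bacteriuria, the expected observed rate runs from 0% (nobody tested) through 5% (a quarter) and 10% (half) to 20% (all). Both the true rate and the share tested are assumptions.

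Severity is low. The enrolment is meant to inform a later powered study on reflux and coil position, and no success criterion here depends on bacteriuria. It is still worth correcting, because it changes what the safety comparison can conclude. A case report form or laboratory manual that is not shown might specify a urine test, and that would remove the point.

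**What to change.** In the primary safety endpoint:

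1. Report bacteriuria as not systematically assessed, and exclude it from the comparison with published rates.
2. For infection, compare only symptomatic UTI that led to testing or treatment, against published rates defined in the same way.
3. Where routine care yields urine results after placement, capture them and report positives over the number of patients tested. Keep this descriptive: patients tested for cause are a selected group, so their rate should not be set against the literature either.

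This changes endpoint wording and denominators only, with no new test, visit or burden for patients. The downside is that one line is lost from the safety comparison.

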Shao et al have studied the relationship between bladder filling and the renal pelvic pressure (RPP) in stented patients, which revealed that RPP has increased mildly during bladder filling and dramatically during voiding indicating urinary reflux and encouraged on early removal of the stents [4]. Another study showed that patients with stents whose distal coils crossing the midline are at higher risk of poststenting morbidities [5].

From a theoretic point, replacing the distal part with a thin material can reduce the bladder irritative symptoms and allow the ureterovesical junction to coapt and thereby, eliminating urinary reflux [6]. The Ureteral Stent Company, LLC (USC) is developing the RELIEFTM Ureteral Stent, a single use, disposable ureteral stent (US) device that will provide the traditional function of allowing the passage of urine from the kidney to the bladder with two design enhancements to improve patient care:

- A low-profile tether through the intramural ureter segment, minimizing the potential of urinary reflux
- Polymeric solid distal coil that minimizes the potential for coil positioning on the trigone, reducing potential of associated bladder spasms and pain.

As presented in the RELIEF™ Ureteral Stent Regulatory Plan, Matrix Report R-40-001.4, the RELIEF™ Ureteral Stent is intended to relieve proximal and middle third obstruction in a variety of benign, malignant and post-traumatic conditions in the ureter. These conditions include stones and/or stone fragments or other ureteral obstructions such as those associated with ureteral stricture, malignancy of abdominal organs, retroperitoneal fibrosis or ureteral trauma, or in association with Extracorporeal Shock Wave Lithotripsy (ESWL). The stent may be placed using endoscopic surgical techniques or percutaneously using standard radiographic technique. The stent is not intended as a permanent indwelling device.

We hypothesize that the RELIEF stent will offer the same function of the traditional stents with the added benefits of 1) prevention of urinary reflux and 2) reduction of irritative bladder symptoms.

Inclusion and Exclusion Criteria

	Inclusion Criteria				
1.	Male and female patients				
2.	Over 18 years of age and willing and able to provide informed consent				
3.	Renal or ureteral stone of 5-25 mm measured on plain abdomen X-ray KUB (Kidney Ureter Bladder) or CT (computed tomography)				

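### The withdrawal rule has no end point, so read literally a urinary tract infection after stent placement (an expected adverse event) is a ground for leaving follow-up

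*Protocol*

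**What the plan says.** Under Withdrawal of Research Participants the protocol states: "Study participants will remain in the trial unless they choose to withdraw or they no longer meet the inclusion or exclusion criteria". The sentence sets no date or event after which eligibility ceases to matter.

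Elsewhere the criteria are treated as a gate at entry. Consent Process has suitability assessed on admission and continues: "If the patient meets the inclusion/exclusion criteria, he/she will enter the study". The Study Timeline marks the inclusion and exclusion criteria in the Day 0 column only.

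The criteria differ in whether they carry their own timing:

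- Inclusion 3 requires "Renal or ureteral stone of 5-25 mm measured on plain abdomen X-ray KUB" or on CT. No timing is given.
- Exclusion 2, "Patients with urinary reflux (assessed by pre-stent cystogram", is tied to a test done before stenting.
- Exclusion 3 covers bilateral stone surgery and active "urinary tract infection (UTI) or sepsis". No timing is given.
- Exclusion 4 is labelled "Intraoperative exclusion".

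UTI is also on the list of expected adverse events and is repeated under Risks to Research Participants. Adverse events form the primary safety endpoint, and the Study Timeline schedules them through the day of stent removal.

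**The concern.** The withdrawal sentence is a rule about staying in the trial, not about getting in. Because it has no end point, it can be applied to a patient who already has the stent. A UTI in the weeks after placement would put that patient in breach of exclusion 3, and the sentence would then end participation. The event that triggers departure is one of the outcomes the trial is meant to count, so any resulting loss would be informative.

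The assessments exposed are those that come after the UTI: later adverse events, the Day 7-30 USSQ (the secondary endpoint), and the removal-day grading of the ureteral orifice and inspection of the stent for encrustation. If infected patients feel worse than the others, losing them would make the stent look better tolerated. That direction is probable but not certain.

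**Working it through.** **Text check.** The protocol contains no figure to reproduce here, so the passages are set against each other.

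1. *Does any passage limit the withdrawal sentence in time?* No. The admission check in Consent Process and the Day 0 column of the Study Timeline govern entry. Neither says that eligibility stops counting afterwards.
2. *Which criteria can change after insertion?* Exclusions 2 and 4 cannot, because each is fixed to a moment before or during the procedure. Exclusion 3 can, through a new UTI or sepsis.
3. *Does the rule as written give a sensible result for the inclusion criteria?* No. The Ureteral Stent Placement steps include "Insert guidewire and perform ureteroscopy for treatment when needed" before the stent goes in. A patient whose stone is cleared at that step no longer has the 5-25 mm stone of inclusion 3. The literal rule would remove that patient because treatment succeeded. A time limit must therefore be intended, but none is written.
4. *Is follow-up protected some other way?* Partly. The data-monitoring section has each reported adverse event documented until it resolves, so the triggering UTI is not lost. The note under the primary effectiveness endpoint keeps data when stenting ends because of pain not associated with the stent. Nothing equivalent covers patients who leave on eligibility grounds.

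**Size.** From the protocol: n = 20 to 30. Assumed, because the protocol gives no values: UTI rate p = 5-15% between placement and removal; infected patients score d = 0.5-1 SD worse on the USSQ; all of them are withdrawn.

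- Expected number affected = n × p.
- Retained r = n × (1 − p).
- Shift in USSQ mean = p × d. The mean of all stented patients is (1 − p)·m + p·(m + d) = m + p·d, and the retained patients show m.
- Standard error in the retained patients, in SD units = 1/√r.

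| n | p | Affected | Retained | SE (SD units) | Shift, d = 0.5 | Shift, d = 1 |
|---|---|---|---|---|---|---|
| 20 | 5% | 1.0 | 19 | 0.229 | 0.025 | 0.05 |
| 20 | 10% | 2.0 | 18 | 0.236 | 0.05 | 0.10 |
| 20 | 15% | 3.0 | 17 | 0.243 | 0.075 | 0.15 |
| 30 | 5% | 1.5 | 28.5 | 0.187 | 0.025 | 0.05 |
| 30 | 10% | 3.0 | 27 | 0.192 | 0.05 | 0.10 |
| 30 | 15% | 4.5 | 25.5 | 0.198 | 0.075 | 0.15 |

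The smallest ratio of shift to standard error is 0.025/0.229 = 0.11 (n = 20, p = 5%, d = 0.5). The largest is 0.15/0.198 = 0.76 (n = 30, p = 15%, d = 1). If only half of the infected patients were withdrawn, the number lost would be 0.5 to 2.25.

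The chance that the question arises at all is 1 − (1 − p)^n. At p = 5% this is 0.64 for n = 20 and 0.79 for n = 30; at p = 10% it is 0.88 and 0.96.

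*Encrustation.* Take n = 20 with 2 withdrawn (p = 10%) and 1 encrusted stent seen among the 18 retained. The observed rate is 1/18 = 5.6%. Among all 20 stented patients the rate could be anything from 1/20 = 5.0% (neither withdrawn patient encrusted) to 3/20 = 15.0% (both encrusted).

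**The case against.** The best reply is that the sentence was never meant to reach past insertion. Strictly, a patient with a new UTI does not cease to meet exclusion 3 but begins to meet it, so the phrase works only as shorthand for being eligible. The protocol's other use of that shorthand concerns entry at admission. No later visit re-checks the criteria. The sentence also has an obvious job between entry and insertion: the pre-stent cystogram, distal-ureter trauma and residual contrast can each remove a patient there, the last with the words "subject may be excluded from study and traditional stent used". Finally, the protocol separates expected from unexpected adverse events and attaches the recruitment hold and stent removal only to the latter. That suggests UTI is an outcome to be observed, not a reason to leave.

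Much of this stands. The pre-insertion meaning is plausible, and under it nothing is lost. But it has to be inferred. The passages relied on govern entry, recruitment holds and stent removal, and none limits the withdrawal sentence. That the literal rule gives absurd results for cleared stones shows that a limit is needed, not that one has been written. Nor can this be left to an analysis plan: who stays in follow-up is a conduct rule, and analysis cannot recover visits that were not made.

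The objection is also right that every rate used above is assumed and that the demonstrated effect is small. That bears on severity, not on whether the wording should be corrected.

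**Conclusion.** The concern holds, as a minor point. The withdrawal rule is broader than it should be, and as written it lets an expected adverse event end follow-up.

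Its practical effect is unknown, because the protocol gives no UTI rate. It ranges from zero, if sites apply the pre-insertion meaning, to about 1-4.5 of 20-30 patients if all infected patients are withdrawn at an assumed rate of 5-15%. The resulting USSQ shift stays below one standard error throughout (0.11 to 0.76) under the assumed 0.5-1 SD difference. The encrustation rate could move either way, and the upper bound of 15.0% requires every withdrawn patient to be encrusted.

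Day 0 reflux and coil-position results are unaffected, and the 48-hour drainage endpoint is exposed only to very early events.

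**What to change.** Reconcile the withdrawal sentence with Consent Process, the Study Procedures and the Study Timeline by stating three things:

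1. The inclusion criteria, such as stone size and location, are judged at admission. A limit at insertion alone would not be enough, because stone treatment comes before the stent is placed.
2. Withdrawal on eligibility grounds after admission, including the pre-stent cystogram and intraoperative exclusions, applies only up to RELIEF insertion.
3. Patients who receive the stent stay in scheduled follow-up and in the safety data even if they later develop a condition named in the criteria, unless they withdraw consent.

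This concerns follow-up and data collection only; clinical care is unchanged. The cost is two or three sentences of protocol wording, with no added visits, patients or procedures.
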